***Revision date: 20/08/2018***

## **Protocol summary**

This study is conducted by a working group of the French Society of Medical Physics (SFPM). Its main aim is to establish reference dose levels for the most common procedures performed in operating rooms using mobile x-ray systems, hence helping medical physicists and surgeons to evaluate their practice and optimize patient radiation protection.

This is a multi-centric prospective study involving 73 medical institutions of different categories (public university hospitals, clinics, cancer centers, etc.). It consists on progressively collecting anonymous data for 15 to 30 procedures from a list of 62 types of procedures, belonging to 7 surgery specialties (neurosurgery, orthopedic, digestive, urology, cardiology, vascular and multi-specialty). Collected data include patient BMI and information about the x-ray equipment, the procedure and the dosimetric parameters. Data collection doesn't require the access to the patient medical record and doesn't impact his medical care.

Proposed dose reference levels will be expressed in terms of KAP (Kerma-Area-Product), fluoroscopy time and air Kerma. Moreover, multiple statistical analyses will be done to investigate the impact of different variables on the procedure X-ray doses.

## **Context:**

Reference dose levels, introduced by the International Commission on Radiological Protection (ICRP) in 1996, are intended to help professionals using medical imaging to evaluate their practice and optimize patient's doses.

European directive 2013/59/Euratom emphasizes the need to establish, use and regularly review reference levels for diagnostic and interventional procedures and to publish guidelines on this topic.

Furthermore, national reference levels were established for conventional radiology and CT exams. They are used as a tool for the optimization of medical practices. Besides, a working group of the French society of medical physicists (SFPM) has published in 2017 reference levels for interventional radiology procedures.

Although radiation protection is a big challenge encountered in operating rooms, few data are available in the literature regarding the use of mobile x-ray equipments.

In this context, the SFPM suggested the creation of a working group in 2017 to establish reference levels for the main procedures realized in the operating rooms using mobile x-ray systems. The aim of this working group is to help medical physicists and surgeons in evaluating their practice and optimizing patient radiation protection. The working group is composed of 5 medical physicists working in 5 different institutions in France.

## **Objectives**

### **Main goal:**

Establish dosimetric reference levels, in terms of KAP (Kerma-Area-Product)

### **Secondary goals:**

- Reference levels in terms of fluoroscopy time and air kerma
- Analysis by the procedures details (impact of different techniques, instruments and materials, etc...)
- Assessing inter-site variability
- Correlation between KAP and BMI, fluoroscopy pulse rate and mode

- Ratio between fluoroscopy and radiography doses
- Effect of zoom and magnification on the dose
- Institution -type distribution of doses
- Impact of the surgical specialty on the doses delivered for some procedures.

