### **Scope of the study**

**Surgical procedures:** a total of 62 procedures (p=62) belonging to 7 different surgery specialties are involved in this study. Selected specialties are neurosurgery (p=12), orthopedic (p=15), digestive (p=6), urology (p=10), cardiology (p=6), vascular (p=11), multi-specialty (p=2). A brief summary of each procedure will be sent to the participating institution.

**Study type and cohort:** This is a multi-centric prospective study which consists on progressively collecting anonymous data for 15 to 30 procedures from a list of 62 procedures. This study is thus equivalent to a retrospective study. It doesn't require any access to patient medical records nor influence his medical care as the data are only provided by the x-ray system or the medical team.

In order to reach a good compromise between satisfactory statistical power and achievable database, 15 to 30 procedures per surgery type and per institution would be suitable for the study. This is consistent with the previous published studies and recommendations (ICRP, French legislation). Moreover, limiting the number of procedures to this range (15-30) will ensure enrollment of homogeneous cohorts between participating institutions.

73 health institutions of different categories (University hospital, clinic, cancer center, etc..) confirmed their participations to the study. Hence, the minimal number of procedure regardless of the procedure type would be 11490 and the maximal number would be 22980.

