#### **Outcomes:**

The main goal of this study is to publish descriptive statistics (mean, standard deviation, median, 1st quartile, 3rd quartile) for each dosimetric data (KAP, fluoroscopy time, kerma, etc..) and for each category of surgery procedures. Results will be presented with a 95% confidence interval.

Moreover, correlation analysis between several variables as indicated previously in the goal section will be done. The differences between detector and equipment technologies will be also studied using appropriate statistical tests.

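### Simple correlation is the only method named for KAP against BMI, pulse rate and mode, with no stated account of procedure type or institution

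*Protocol*

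**What the plan says.** Under Secondary goals, the protocol lists "Correlation between KAP and BMI, fluoroscopy pulse rate and mode". The Outcomes section refers back to that list: "correlation analysis between several variables as indicated previously in the goal section will be done". No coefficient is named, and nothing is said about stratifying or adjusting these analyses.

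Three other statements bear on how this should be read:

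- The Protocol summary announces that "multiple statistical analyses will be done to investigate the impact of different variables on the procedure X-ray doses".
- The Outcomes section gives descriptive statistics "for each category of surgery procedures". That phrase belongs to the descriptive results and is not extended to the correlations.
- "Assessing inter-site variability" is a goal of its own, not an adjustment of the correlations.

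On structure, the Scope section states that "a total of 62 procedures (p=62) belonging to 7 different surgery specialties are involved in this study", that "73 health institutions of different categories" take part, and that "15 to 30 procedures per surgery type and per institution would be suitable for the study". The Data collection section lists fluoroscopy mode and pulse rate as separate items, gives no coding for mode, and makes weight and height optional.

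**The concern.** Pulse rate and mode are equipment settings. They plausibly differ between procedure types and between institutions, and KAP differs between both for many other reasons. A simple correlation cannot separate the setting from the type or site in which it is used. Records from one institution also resemble each other, so the effective sample is smaller than the record count.

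The protocol's purpose is to help medical physicists and surgeons optimise practice, and its summary speaks of impact on dose. A reader will therefore take a pulse-rate coefficient as guidance. A distorted estimate could hide a dose saving or exaggerate one, and an interval that is too narrow would make either look well established.

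**Working it through.** The protocol gives no expected correlation, variance or power for these analyses, so there is no stated figure to reproduce. The checks below are illustrative, and every variance and association in them is assumed.

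**Structure from the documents.** Types: 12 + 15 + 6 + 10 + 6 + 11 + 2 = 62. Institutions: 73. Records per type and institution: 15 to 30. The stated minimum total, 11490, divided by 15 gives 766 institution-by-type cells. The protocol does not state 766; it is implied. Per type, 766 / 62 = 12.4, or about 12 institutions.

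**Check 1: correlations pooled over types.** A simulation used 766 cells of 15 records, with 200 runs per scenario. Assumed for log KAP: slope +0.2, residual SD 0.8, site SD 0.5, between-type SD 0.5 to 1.5. The BMI-like predictor has SD 0.5 between types and 1 within; the pulse-rate-like predictor has 1 and 0.5. The type-level correlation is that between the type components of the predictor and of log KAP. Results for between-type SD 1.0:

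| Predictor | Type-level correlation | Mean pooled r | Runs with negative pooled r | Mean within-type r |
|---|---|---|---|---|
| BMI-like | +0.3 | 0.253 | 0% | 0.209 |
| BMI-like | 0 | 0.162 | 0% | 0.210 |
| BMI-like | -0.3 | 0.060 | 9% | 0.210 |
| BMI-like | -0.6 | -0.031 | 77% | 0.209 |
| Pulse-rate-like | +0.3 | 0.332 | 0% | 0.107 |
| Pulse-rate-like | 0 | 0.145 | 4% | 0.106 |
| Pulse-rate-like | -0.3 | -0.027 | 64% | 0.106 |
| Pulse-rate-like | -0.6 | -0.233 | 100% | 0.108 |

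Over all between-type SDs, the mean pooled r ran from 0.264 to -0.092 (BMI-like) and from 0.345 to -0.339 (pulse-rate-like). The within-type r stayed near 0.21 and 0.11. A sign change is thus possible, but it needs both pooling and an opposite association at type level. With a type-level correlation of 0 or +0.3, the mean pooled r kept its sign.

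**Check 2: correlations within one type.** Take 12 institutions with 15 cases each and no true effect of pulse rate. Assume a within-site SD of log KAP of 0.8 and an institution SD s.

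- Intraclass correlation of log KAP: ICC = s² / (s² + 0.8²). For s = 0.4: 0.16 / (0.16 + 0.64) = 0.2.
- Variance inflation of the simple correlation: D = 1 + (15 - 1) × ICC × f, where f is the share of the pulse-rate variance that lies between sites. For f = 1: 1 + 14 × 0.2 = 3.8.
- False-positive rate, approximately: 2 × [1 - Φ(1.96 / √D)]. For D = 3.8: √D = 1.949, 1.96 / 1.949 = 1.005, rate 31%.

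| Institution SD | ICC | Share f | D | False-positive rate |
|---|---|---|---|---|
| 0.4 | 0.20 | 1 (fixed within site) | 3.80 | 31% |
| 0.4 | 0.20 | 0.5 | 2.40 | 21% |
| 0.4 | 0.20 | 0.2 | 1.56 | 12% |
| 0.2 | 0.059 | 1 | 1.82 | 15% |
| 0.6 | 0.36 | 1 | 6.04 | 43% |

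Simulation of the same five cases gave 32%, 20%, 12%, 16% and 44%, against a nominal 5%. With s = 0.2 and f = 0.2 the formula gives only 7%, and with f = 0 there is no inflation. So the size depends on how far pulse rate is a site setting, which the protocol does not say.

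**Check 3: mode.** Mode is listed apart from pulse rate and without a scale. If it has more than two unordered levels, any numeric coding is arbitrary and so is the coefficient.

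**The case against.** The strongest reply is that the text is brief, not wrong. A reader might infer that the protocol commits itself to unadjusted coefficients, one variable at a time, pooled over all 62 types, so that the result is confounded and will reverse. The documents do not support that. They do not say bivariate, unadjusted or pooled. The summary's promise of multiple analyses leaves room for a multivariable model, and the by-category descriptive results make a within-type correlation at least as natural a reading. Confounding by type is therefore a conditional risk, and the protocol contains no data that show it.

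It is also fair to say that model details for a secondary goal usually go in the analysis plan, which is not at hand. That disposes of any complaint about missing detail. It does not dispose of the choice that is stated: correlation is named in two places, whereas the Outcomes section leaves the test open for comparisons of detector and equipment technologies.

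For mode, a two-level variable allows a point-biserial coefficient and an ordered one a rank coefficient, so the objection to correlation holds only for unordered categories. The sentence on 95% confidence intervals follows the descriptive statistics and may not have been meant for the correlations. The clustering problem then applies to whatever interval or test accompanies them.

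Finally, a remedy cannot assume complete data. Weight and height are optional, no identifier for the x-ray unit is listed, and a random institution intercept alone does not remove site confounding when the setting itself varies by site. All of this stands, and the fix allows for it.

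**Conclusion.** The point holds in conditional form. Correlation is the only method named for these three variables, and no account of procedure type or institution is stated. Under either reading of the text a weakness remains. Pooled, the estimate is open to confounding by type and can reverse if the type-level association runs the other way. Within type, simple intervals are likely too narrow (about 12% to 44% false positives in the cases simulated, less if pulse rate hardly differs between sites), and site confounding is untouched. These sizes rest on assumed variances and associations, not on figures in the protocol. The change is worth making because the results are meant to inform practice, but it concerns one secondary goal and leaves the primary KAP reference levels as they are.

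**What to change.** Replace or supplement the correlations with a regression of log KAP:

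- Procedure type as a fixed effect, pulse rate, and fluoroscopy mode as a factor.
- Institution accounted for by institution fixed effects, or by a random intercept with pulse rate split into its within-site and between-site parts.
- Results as percent change in KAP, 100 × (exp(b) - 1) for coefficient b, with 95% confidence intervals.
- The BMI term fitted in records that have weight and height, with the number missing reported. Pulse-rate and mode results also given without BMI, so that records are not lost.
- No random effect for the x-ray unit unless a unit identifier is recorded.

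Pulse rate and mode are already on the collection list, procedure type defines the sampling, and each institution sends its own file, so the core model needs no new data. The costs are a little more analysis work, percent changes in place of correlation coefficients, and less precision for settings that hardly vary within a site. The model also imposes a common slope across types unless an interaction with type is checked.

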### **Inclusion criteria:**

- Fluoroscopy guided procedures performed on adult patients ( $\geq 16$  years old)
- Fluoroscopy guided procedures performed on mobile x-ray systems. Procedures performed outside of the operating rooms using mobile x-ray systems are included in this study
- Fluoroscopy guided procedures performed using mini C-arms or O-arms
- 

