### **Data collection**

Data will be collected using a password-protected Excel spreadsheet. This excel file will be sent to all the participating institutions at the beginning of data collection. Every institution will send the excel file completed with anonymized data to the scientific responsible of the study through the secure email server of the APHP institution. Data collection period is set to 6 months.

Collected data have been organized into 4 categories:

- Data regarding the x-ray equipment and available on the quality controls (QC) reports : Year of construction, image detector type, size of the smaller field,

difference between the displayed and measured KAP for the smallest field, size of the biggest field, difference between the displayed and measured KAP for the biggest field, size of the largest field adapted to the size of the phantom, difference between displayed and measured air kerma available in the last QC report, date of the last external QC previous to the procedure. Also, participating institution should precise whether if the x-ray equipment was connected to a Dose Archiving and a Communication system (DACS)

- Data regarding the patient (Optional) : Weight and height (provided from the equipment or given by the medical team)
- Data regarding the procedure: specialty, additional information about the procedure, size of the most used field for the concerned procedure. These data are provided by the medical team.
- Technical and dosimetric data available on the x-ray equipment : total KAP, Total air kerma, total number of image frames, fluoroscopy mode, fluoroscopy pulse rate, fluoroscopy time, dosimetric data specific to the O-arm equipment.

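### The fluoroscopy-to-radiography dose ratio is a secondary goal, but the protocol's data list names procedure doses only as totals

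*Protocol*

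**What the plan says.** Under Objectives, the main goal is reference levels in KAP. Eight secondary goals follow, and one is "Ratio between fluoroscopy and radiography doses". Nothing more is said there about how the ratio is defined or obtained.

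The Data collection section sets out four categories of data. For each procedure, the technical and dosimetric category names "total KAP, Total air kerma, total number of image frames, fluoroscopy mode, fluoroscopy pulse rate, fluoroscopy time" and then "dosimetric data specific to the O-arm equipment". The content of that last entry is not described. O-arms are in scope, since the inclusion criteria admit "Fluoroscopy guided procedures performed using mini C-arms or O-arms".

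On sources, Scope of the study states that "the data are only provided by the x-ray system or the medical team". On timing, "This excel file will be sent to all the participating institutions at the beginning of data collection". The Outcomes section promises descriptive statistics "for each dosimetric data (KAP, fluoroscopy time, kerma, etc" and so on; it names no dose by exposure mode, although its list is left open.

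**The concern.** A ratio of two doses needs both doses. The protocol sets the ratio as a goal, yet the only procedure doses it says it will record are sums over both exposure modes. An analysis plan can choose a model, but it cannot supply a dose component that nobody wrote down.

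If the form matches the list, the study would reach analysis with no measured ratio for standard C-arms. Completed records would then be hard to repair. The section on study approval and consent says that patients are given no codes, so a finished spreadsheet row could not readily be traced back to its examination. The Data collection section asks whether the equipment is connected to a dose archive. The documents do not say whether such an archive keeps the split, or how an anonymous row would be matched to it.

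**Working it through.** The protocol gives no figure to reproduce for this goal. The check compares the goal with the listed variables and asks whether they determine the ratio.

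**Inputs.** The technical and dosimetric category has seven entries:

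| Type of entry | Entries | Count |
|---|---|---|
| Procedure dose, as a total | KAP; air kerma | 2 |
| Count of images | image frames | 1 |
| Fluoroscopy settings and time | mode; pulse rate; time | 3 |
| Unspecified | O-arm data | 1 |

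2 + 1 + 3 + 1 = 7. None is named as a fluoroscopy dose or a radiography dose. KAP and air kerma also appear among the quality-control items, but there they are differences between displayed and measured values. Those describe the equipment, not the dose of a procedure.

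**From the total alone.** Let F be the fluoroscopy KAP, R the radiography KAP and T = F + R the recorded total. The target is F / R. This is one equation in two unknowns. With an assumed T = 10 (arbitrary units, not from the protocol):

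- F = 8, R = 2: ratio 8 / 2 = 4
- F = 5, R = 5: ratio 5 / 5 = 1
- F = 2, R = 8: ratio 2 / 8 = 0.25

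All three give the same recorded value. Air kerma is also recorded only as a total, so it brings its own unknown split.

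**Adding fluoroscopy time and frame count.** Write F = a × t and R = b × n, where t is fluoroscopy time, n the number of radiographic images, a the KAP per unit of time and b the KAP per image. Neither a nor b is listed. In a single record with T = 10, the choice a = 8/t, b = 2/n fits exactly, and so does a = 2/t, b = 8/n. One record therefore still leaves the ratio open.

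**Across many records.** If a and b can be treated as common within a group of procedures, and t and n do not move in step, regressing T on t and n estimates both. The aggregate ratio is then (a × sum of t) / (b × sum of n). This is a modelled average, not a measurement. It also requires n to count radiographic images only. If n includes images taken from fluoroscopy, b × n is not the radiography dose. The protocol does not define the term.

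**Records with no frames.** On the radiographic reading, a record with n = 0 is fluoroscopy only, and its total KAP is a fluoroscopy dose. It has no radiography dose and gives no ratio by itself.

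**The case against.** The strongest objection is that an item missing from a prose summary need not be missing from the form. The spreadsheet is the working instrument and is not shown. The summary also has no explicit item for procedure type, although results are to be reported by category of procedure, so the list is probably not exhaustive. This stands, and it makes the consequence conditional. It does not remove the mismatch: the category calls both doses totals and, unlike the Outcomes list, is not left open-ended.

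A second objection is that the goal nowhere demands a measured ratio for each record. An aggregate estimate could come from total KAP, time and frame count over the 11490 to 22980 planned procedures, and the choice of model belongs in an analysis plan. This stands in part. The lack of a described model is no fault of the protocol. But the estimate depends on what the frame count means, and that is a matter of data definition that no later model can settle.

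Three stronger readings are tempting and are not supported:

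- A reader might infer that this is the only secondary goal without a listed item. Total KAP, time and frame count do relate to it, so no such claim is made. Equally, some other goals rest on information outside the list: institution type, for example, can be known from the sender, because "Every institution will send the excel file completed with anonymized data".
- A reader might infer that the bar on access to medical records is what prevents repair. Dose data come from the x-ray system, so the relevant obstacle is the absence of patient codes.
- A reader might infer that the split is certainly not being collected. The documents do not show that.

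**Conclusion.** The point holds in a limited form, and its severity is minor. As described, the data list does not support a measured fluoroscopy-to-radiography dose ratio on standard C-arms. At most it supports a model-based aggregate estimate, provided that image frames are radiographic images. Whether the O-arm entry would serve O-arms cannot be told.

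The size is one descriptive secondary goal of eight. The main goal needs only total KAP and is unaffected. The documents do not give the number of standard C-arm records, so no share of records is claimed. The conclusion assumes that the spreadsheet follows the Data collection section; if it already holds the split, the defect is only an incomplete list.

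**What to change.** Before the spreadsheet is sent out, add fluoroscopy KAP and radiography KAP to the technical and dosimetric list, with the matching pair for air kerma where the system displays it. Allow an explicit entry for values that are not displayed. Compute the ratio only in records where both parts are recorded, and report how many records and which equipment types contribute. If the form already has these fields, name them in the Data collection section.

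If the split will not be collected, restate the goal as a model-based estimate and define image frames, or delete the goal.

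The cost is two to four spreadsheet columns (one pair for KAP, and a second pair for air kerma), or one changed line. The downsides are some extra entry work at up to 73 institutions and a ratio that may rest on a selected subset of equipment, since the documents do not say how many mobile systems display the split. They also do not say whether added dose columns would need notice to the bodies that approved the study; this should be checked.
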